In order to assess target plaque lesions, the inner and outer contours of the vessel will be determined independently and blinded for the time of the exam (i.e., dates of scans will be masked for analysis and order of performance mixed). For comparison an index lesion will be selected (based on largest non-calcified plaque component and sufficient image quality on both exams). Using proprietary software developed in conjunction with the software manufacturer, both vessels will be visually aligned based on anatomical landmarks and the lesion will be selected on both exams (baseline and follow up). The software provides the volume measurements for each lesion.

An improved tool for the co-registration step (fully automatic co-registration) is under development and may also be used.

CARDIAC MRI (CMR) (OPTIONAL)

CMR will be performed using a high field (1.5 or 3T) scanner. The aim of the cardiac study is to a) identify high signal intensity T1 coronary artery plaque. The CMR protocol will include localization images with coronary CMR to localize plaque volume. Myocardial structure, function and tissue composition will be performed per NIH Clinical Center standard protocol for comprehensive phenotyping to characterize subclinical disease that may be present. In a population of middle and older adults in the U.S.,

approximately 9% of study subjects have evidence of myocardial damage defined by myocardial scar or abnormalities in cardiac wall motion (Turkbey et al, JAMA 2015, 314(18)); of myocardial scars, approximately 80% are undetected by clinical correlation/ ECG (Barbier, Bjerner et al. 2006, Schelbert, Cao et al. 2012).

18F NAF PET IMAGING

For 18F-NaF uptake, the coronary arteries are visually identified, and regions of interest will be drawn around areas of maximal uptake in the left main stem, left anterior descending artery, circumflex artery, and the right coronary artery. The maximum standard uptake value (SUV) is recorded from these regions. The SUV is the decay-corrected tissue concentration of 18F-NaF divided by the injected dose/body weight. However, SUV measurements in vascular structures are influenced by variability in 18F-FDG and 18F-NaF activity in the blood. Therefore, SUV measurements are divided by an averaged mean SUV value in the blood pool, derived from 5 circular regions of interest drawn in the center of the superior vena cava. This provides maximum tissue/background ratios (TBRs) as a measure of arterial tracer uptake.

2. ELIGIBILITY ASSESSMENT AND ENROLLMENT

2.1. INCLUSION CRITERIA

- A. Men \geq 40 and \leq 75 years of age; women \geq 40 and \leq 75 years of age
- B. Willing to travel to the NIH for follow-up visits.
- C. Willing to start or modify statin therapy.
- D. Able to understand and sign informed consent.
- E. Serum Creatinine \leq 1.5 mg/dL within 30 days in accordance with the NIH Clinical Center Radiology and Imaging Sciences SOP. (http://intranet.cc.nih.gov/radiology/policies/ct_iv_contrast_sop.html)
- F. Eligible for primary prevention statin therapy
 - 1) Eligible for at least moderate intensity statin according to 2013 ACC/AHA GRCR (i.e., \geq 5% 10 year cardiovascular risk, https://my.americanheart.org/professional/StatementsGuidelines/Prevention-Guidelines_UCM_457698_SubHomePage.jsp) **OR**
 - 2) low ($<5\%$) 10 year cardiovascular risk per 2013 ACC/ AHA and with coronary artery calcium score \geq 300 Agatston units or \geq 75 percentile for age, sex, and ethnicity determined per MESA study (<http://www.mesa-nhlbi.org/calcium/input.aspx>).

2.2. EXCLUSION CRITERIA

- A. Allergy or prior clinically relevant adverse reaction to Rosuvastatin (does not include minor muscle pain).
- B. High intensity statin treatment for more than 90 days prior to enrollment
- C. LDL \geq 190 mg/ml
- D. Physician-diagnosed heart attack
- E. Physician-diagnosed stroke or TIA
- F. Physician-diagnosed heart failure
- G. Having undergone procedures related to cardiovascular disease (CABG, angioplasty, valve replacement, pacemaker or defibrillator implantation, any surgery on the heart or arteries)

- H. Active treatment for cancer
- I. Prior hypersensitivity reaction to iodinated contrast injection
- J. Known hyperthyroidism.
- K. Acute renal failure, renal transplant, dialysis and renal failure clinically diagnosed.
- L. History of liver transplant or severe liver disease or unexplained elevation of baseline ALT>3x upper limit of normal
- M. Pregnancy and nursing
- N. Mental, neurologic or social condition preventing understanding of the rationale, procedures, risks and potential benefits associated with the trial.
- O. Any other conditions that precludes safety for MRI and/or CT imaging per the researcher's evaluation.
- P. Individuals with hemoglobinopathies or severe asthma.
- Q. Severe renal excretory dysfunction, estimated glomerular filtration (eGFR) rate < 30 mL/min/1.73m² body surface area according to the Modification of Diet in Renal Disease criteria
Glomerular filtration rate will be estimated using the MDRD 2005 revised study formula:
eGFR (mL/min/1.73m²) = 175 x (standardized serum creatinine)-1.154 x (age)-0.203 x 0.742 (if the subject is female) or x 1.212 (if the subject is black)

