All participants will be screened for their willingness/ability to participate in the various study procedures (see Appendix for MRI screening questionnaire) and those unwilling/unable to participate in a specific procedure will be excluded from that study. Prior to enrollment onto the study, potential research subjects will be sent a Study Questionnaire form to assist the research team in confirming diagnosis and determining which tests will be appropriate for the subject (see appendix E). The questionnaire will also guide medical record gathering prior to the visit to aid consultants. The initial screening visit will consist of laboratory evaluation initial laboratory assays in addition to a focused clinical exam and history. The objectives of the screening visit are a) exclude any contraindication for CCTA, nitrates or beta blockers (e.g. history of hyperthyroidism, aortic stenosis or prior use of sildenafil); b) determine lipid levels and c) determine if noncalcified plaque is present. Study subjects already receiving high intensity therapy for more than 90 days prior to enrollment will not be considered. Study subjects will be eligible for at least moderate statin therapy according to ACC/AHA 2013GRCR criterion and 2018 ACC/AHA guidelines. Note that study subjects at low GCRC cardiovascular risk (using traditional risk factors) but with CAC score > 75th percentile for age, gender and ethnicity will be classified to be moderate risk. Specific inclusion/exclusion criteria are indicated in Sections 2.1 and 2.2 below.

If a) noncalcified coronary plaque is identified on CCTA, and b) the study subject qualifies for at least moderate statin therapy, the study subject will be enrolled for statin therapy and follow-up. Only study subjects with a noncalcified plaque component extending over 4 mm will be considered for further follow-up in the study.

IMAGING - OVERVIEW

Imaging consists of CCTA for plaque evaluation at baseline, 12 months 24 months, and 36 months. Cardiac MRI may be performed at baseline, and 24 months (optional). A clinical report of imaging and lab results will be offered to all subjects and – if requested by the subject – can be sent to a physician.

A study of F18 NaF PET imaging will be conducted; participation in the PET study will be considered to be optional for participants. Lack of participation will not exclude subjects from the study cohort.

CT IMAGING

CT Imaging protocol

1. Coronary calcium scan

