5.2 Liver Enzyme Abnormalities and Monitoring It is recommended that liver enzyme tests be performed before and at 12 weeks following both the initiation of therapy and any elevation of dose, and periodically (e.g., semiannually) thereafter. Increases in serum transaminases [AST (SGOT) or ALT (SGPT)] have been reported with HMG-CoA reductase inhibitors, including CRESTOR. In most cases, the elevations were transient and resolved or improved on continued therapy or after a brief interruption in therapy. There were two cases of jaundice, for which a relationship to CRESTOR therapy could not be determined, which resolved after discontinuation of therapy. There were no cases of liver failure or irreversible liver disease in these trials. In a pooled analysis of placebo-controlled trials, increases in serum transaminases to >3 times the upper limit of normal occurred in 1.1% of patients taking CRESTOR versus 0.5% of patients treated with placebo. Patients who develop increased transaminase levels should be monitored until the abnormalities have resolved. Should an increase in ALT or AST of >3 times ULN persist, a reduction of dose or withdrawal of CRESTOR is recommended. CRESTOR should be used with caution in patients who consume substantial quantities of alcohol and/or have a history of chronic liver disease [see Clinical Pharmacology (12.3)]. Active liver disease, which may include unexplained persistent transaminase elevations, is a contraindication to the use of CRESTOR [see Contraindications (4)].

5.3 Concomitant Coumarin Anticoagulants Caution should be exercised when anticoagulants are given in conjunction with CRESTOR because of its potentiation of the effect of coumarin-type anticoagulants in prolonging the prothrombin time/INR. In patients taking coumarin anticoagulants and CRESTOR concomitantly, INR should be determined before starting CRESTOR and frequently enough during early therapy to ensure that no significant alteration of INR occurs [see Drug Interactions (7.4)].

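### Exclusion L lets in active liver disease that is not severe, which the protocol's own rosuvastatin label text contraindicates, and at entry it counts ALT but not AST

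*Combined protocol and SAP*

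**What the plan says.** Exclusion L in section 2.2 has three triggers: "History of liver transplant or severe liver disease or unexplained elevation of baseline ALT>3x upper limit of normal". No other exclusion mentions the liver.

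The rosuvastatin package insert in section 9, under its item 5.2 on liver enzymes, states: "Active liver disease, which may include unexplained persistent transaminase elevations, is a contraindication to the use of CRESTOR". It treats the two transaminases alike: "Should an increase in ALT or AST of >3 times ULN persist, a reduction of dose or withdrawal of CRESTOR is recommended". For past rather than current disease it asks only for care: "CRESTOR should be used with caution in patients who consume substantial quantities of alcohol and/or have a history of chronic liver disease".

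Section 2.4 has eligible subjects begin treatment, and section 3.2 sets rosuvastatin 40 mg as the target dose. Section 3.2 also says that the drug is paused and the test repeated within two weeks if ALT, AST or alkaline phosphatase exceeds three times ULN without liver symptoms. Restarting is left to clinical judgment.

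**The concern.** Eligibility criteria should carry the contraindications of the study drug. Here the entry rule uses a higher bar (*severe*) than the label text printed in the same protocol (*active*), and it tests one transaminase where the label text and the trial's own pause rule use both. A site that applies section 2.2 exactly as written could give a high-dose statin to a person for whom section 9 says it should not be used. What is at stake is the safety of individual participants at entry. Nothing here bears on the estimate, the error rate or the sample size.

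**Working it through.** No arithmetic applies. The check sets L against the label text in section 9, then looks for any other rule that acts before the first dose.

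**Step 1. Compare the two texts by type of candidate.**

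| Candidate | Label text, section 9 | Exclusion L |
|---|---|---|
| Active liver disease, not severe, ALT at or below 3x ULN | Contraindicated | Not excluded: no trigger met |
| Active liver disease, not severe, ALT above 3x ULN because of it | Contraindicated | Not excluded: the elevation is explained |
| Unexplained persistent ALT elevation, at or below 3x ULN | May count as active disease | Not excluded |
| Isolated unexplained AST above 3x ULN | May count, if persistent | Not excluded: ALT only |
| Single unexplained ALT above 3x ULN | Not shown to be contraindicated | Excluded |
| History of chronic liver disease, not active | Caution only | Not excluded |

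The first two rows are the firm gap. They need no reading of the label's permissive wording about enzyme elevations. The third and fourth rows depend on that wording. The fifth shows that the criteria are not nested: L is stricter than the label text in one respect, and also in barring any liver transplant history.

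**Step 2. Look for another entry rule that covers the first two rows.**

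- Inclusion F is headed "Eligible for primary prevention statin therapy", but its two sub-items are a cardiovascular risk threshold and a calcium score threshold.
- Exclusion A concerns earlier reactions to rosuvastatin.
- Exclusion O, the one exclusion that turns on the researcher's own evaluation, is limited: "Any other conditions that precludes safety for MRI and/or CT imaging".
- The screening objectives under Overview of Enrollment are to "exclude any contraindication for CCTA, nitrates or beta blockers", to measure lipids and to look for noncalcified plaque. Statins are not named.
- Section 2.3 D records diagnoses but singles out only asthma, for beta blockers.
- The Appendix E questionnaire asks about kidney disease and hyperthyroidism by name. Liver disease could surface only under its general question on other medical problems.

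None of these bars the candidate.

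**Step 3. Compare the AST rule at entry with the AST rule on treatment.** At entry, L applies the 3x ULN limit to ALT alone. On treatment, section 3.2 applies it to AST as well. A candidate with isolated unexplained AST above the limit passes L and starts the drug with a value that would pause it in someone already treated. The next scheduled liver tests are at 3 months. This mismatch stands however the label is read.

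**Step 4. Ask whether the on-treatment rules make up for it.** Section 3.4.1, criterion 3, ends treatment for a persistent elevation above 3x ULN only when nothing other than the statin explains it, and pre-existing liver disease would supply another explanation. The closing sentence of criterion 4 is broader. It requires discontinuation for any other relevant abnormality that cannot confidently be ruled out as an effect of study medication. That would catch some of these patients, especially if enzymes rise on drug. It is weaker for a stable abnormality that predates dosing, and like the pause rule it works only after exposure.

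**The case against.** The contraindication is not missing from the protocol: section 9 prints it for whoever prescribes the drug. Before dosing there is a focused history and examination, record gathering and recording of diagnoses, and section 3.2 B calls for liver tests. A careful investigator would probably notice active liver disease, and the mandatory sentence in section 3.4.1 is a real backstop. The boundary is also partly a matter of judgment, since neither *severe* nor *active* is defined and the label text tolerates a history of chronic liver disease. All of this stands, and it makes the risk per patient low. It does not supply an entry rule: the tests and diagnoses are collected, but section 2.2 gives no instruction to act on them in the cases at issue.

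Three stronger readings are tempting and are not supported.

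- A reader might infer that isolated AST above 3x ULN is itself a contraindication. The label text says only that active disease *may* include such elevations, and only persistent ones. A single baseline value does not establish that.
- A reader might infer that the gap contradicts section 7.5, which says that the study is not meant to test statins in new populations. That is a statement of intent, and an incidental enrolment does not contradict it.
- A reader might size the gap from the label's pooled trials, where transaminases above 3x ULN "occurred in 1.1% of patients taking CRESTOR versus 0.5% of patients treated with placebo". The placebo figure would give 190 x 0.005 = 0.95, about one participant. But it is an on-study rate, not a baseline prevalence. It can include unexplained ALT elevations of the kind L already excludes, and it leaves out active disease with enzymes at or below the limit. It does not measure this gap.

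**Conclusion.** The point holds in two parts of unequal strength. First, and firmly, exclusion L admits candidates with active liver disease short of severe, including those whose high ALT is explained by it, although the label text in section 9 contraindicates rosuvastatin for them. Second, L's restriction to ALT is out of step with the pause rule in section 3.2.

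The size cannot be estimated, because the documents give no prevalence for either group among candidates; it is probably small. The conclusion assumes that sites apply section 2.2 as written and that *severe* in L means something narrower than *active* in section 9, which is the ordinary reading of the two words. It is a safety point at entry that merits a wording change.

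**What to change.** Reword L in three moves:

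1. Keep the liver transplant and severe liver disease triggers.
2. Add *active liver disease, including unexplained persistent transaminase elevation*. *Persistent* can be defined as present on two tests before the first dose.
3. Change the enzyme trigger to unexplained baseline *ALT or AST* above 3x ULN.

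Leave a mere history of chronic liver disease eligible with caution, as section 9 advises. Optionally, name active liver disease beside asthma in section 2.3 D, as a contraindication to rosuvastatin.

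The cost is one line of amendment text. Section 3.2 B already calls for liver tests before the drug is started, so the added burden is an occasional repeat test. A few candidates will become ineligible.

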2.3. SCREENING EVALUATION

On-Study Assessments:

Study activities below (see Appendix A for overview) specify the required study tests and procedures for participants. A Telehealth platform visit may be utilized to review subject eligibility at baseline visit in accordance with the NIH-approved telehealth policy.

Baseline visit tests and procedures will be completed within 4 weeks before the first dose of study medication, unless otherwise noted. Results from procedures and laboratory tests from other NIH IRB approved protocols that subjects may have participated in within 4 weeks of enrollment in this study may be used as part of the screening evaluation for this study. At the baseline visit, the Investigator and/or study staff will:

- A. Review the study procedures and determine that the eligible patient is willing to comply with all protocol requirements;
- B. Review the inclusion and exclusion criteria with the patient and determine if the patient can be a participant in the study;
- C. Record previous and concomitant medications, including vitamin and herbal supplements for the 4 weeks before study start.

Special consideration of drug interaction is necessary in the following context: In regard to interaction with CT associated medications (beta blocker, calcium antagonists, Nitroglycerin): **Phosphodiesterase inhibitors (e.g. Viagra), antiarrhythmic drugs.**

Special consideration of drug interaction with Rosuvastatin: **Coumadin, Niacin, Fenofibrate, Colchicine.**

- D. Record known diagnoses. Relevant in the context of study associated medications: **Asthma (contraindication for beta blocker use)**
- E. Record vital signs, height and weight (at Baseline visit)

F. Collect blood and complete laboratory screening and or clinical evaluations that may include the following:

- Fasting lipid panel
- Whole blood serum creatinine
- Complete blood count (CBC),
- Chemistry Labs: Electrolyte Panel, Creatinine, eGFR, Aspartate Amino-Transferase (AST), Alanine Aminotransferase (ALT), Creatine kinase (CK), hsCRP
- HbA1c, fasting glucose
- C-reactive protein (CRP)
- Lipoprotein profile
- Urine pregnancy test (for women of childbearing age)
- Other laboratory measures available in CRIS that may be required to ensure participant safety
- Research blood (10 mL)

G. Baseline CT is performed.

H. Review baseline CT study for regarding continuation of study (presence of CAD):

- Noncalcified plaque component extending over 4 mm
- Study subject must be either 1) at least moderate 10 year cardiovascular risk according to ACC/AHA 2013 criteria OR 2) low risk ACC/AHA risk and CAC score ≥ 300 or $\geq 75^{\text{th}}$ percentile for age, gender and ethnicity.

I. If accepted into study for follow up:

- Cardiac MRI (optional)
- PET study (optional)

J. Perform follow-up lipid panel, creatine kinase and liver function testing at 3 months.

Scheduled study visits which are part of the trial expected procedures will be made by one of the Investigators including the Nurse Coordinator. Clinical follow up will be made at the time of one of the scheduled clinic visits or in response to notification of any perceived clinical alteration.

We expect a some subjects will have ongoing statin treatment when screened for eligibility. We will allow an estimation for the native LDL based on the following statin efficacy chart by multiplying the measured LDL with the correction factor that corresponds to the current statin drug and dosage (source: FDA website).

Atorva	Fluva	Pitava	Lova	Prava	Rosuva	Vytorin†	Simva	% \downarrow LDL-C	Correction Factor
----	40 mg	1 mg	20 mg	20 mg	----	----	10 mg	30%	1.43
10 mg	80 mg	2 mg	40 or 80 mg	40 mg	----	----	20 mg	38%	1.61

20 mg	----	4 mg	80 mg	80 mg	5 mg	10/10 mg	40 mg	41%	1.69
40 mg	----		----	----	10 mg	10/20 mg		47%	1.89
80 mg	----		----	----	20 mg	10/40 mg	----	55%	2.22
	----		----	----	40 mg		----	63%	2.70

2.4. REGISTRATION PROCEDURES

Upon completion of the screening process, eligible subjects will be enrolled on the study and will begin treatment.

3. SUBJECT IMPLEMENTATION

3.1 STUDY DESIGN

This is an interventional trial in which 190 adult men and women will receive high intensity statin treatment. The study duration will be when subjects complete their 36 month visit.

3.2 PROTOCOL EVALUATION/STUDY CALENDAR

Treatment:

High intensity statin therapy:

- High intensity lipid lowering therapy: rosuvastatin, target dose 40 mg (Nicholls et al., 2011).
- If the drug is not tolerated by a patient during the study, alternatives are rosuvastatin 20 mg or atorvastatin 80 mg. Statin dose will be reduced if the serum LDL is below 25 mg/dL (Everett, Mora et al. 2014)

Failure to meet target therapies will not result in removal from the study but will instead be assessed on an intention-to-treat basis.

Protocol Evaluation:

A. Study Subjects will have a study visits for imaging at baseline, 12, 24 and 36 months, 18 and 30 month assessments will be done via telephone, Telehealth platform and or e-mail (**Appendix A, Study Calendar**).

Note: After Amendment O Protocol dated 7/02/2020- no longer enrolling in sub-studies: The PET study subjects will have additional visits. Up to 60 subjects will be accrued to the PET sub study. 30 subjects will be asked to return within 30 days for repeat visit to insure CCTA data reproducibility. Visits will follow the Protocol Evaluation schema in Appendix A. Visits will occur within +/- 12 weeks due for unforeseen events.

B. Clinical Laboratory Measures will be done before starting study drug at baseline enrollment then as clinically indicated per Safety Announcement by the FDA 2.28.2012:

- Serum creatinine kinase, lipid panel and liver function tests will be measured at baseline enrollment and at 3 months after start of drug treatment and annually thereafter when clinically indicated.

- If symptoms indicating possible muscle or liver alterations appear (muscle pain, fatigue, jaundice, abdominal pain, anorexia) the study drug will be paused and a timely evaluation including lab testing for liver and muscle enzymes will be recommended and offered. Depending on the results of the evaluation the drug can be resumed (if association with statin is unlikely), reduced or stopped (based on clinical judgment).
- HbA1c will be measured during the course of the study.
- Urine HCG test for women of childbearing age. Blood glucose measurements also prior to PET imaging.
- Review of interim medical history and evaluation for interim adverse events, off treatment or off study criteria. Complete review and recording of participant medications including over the counter and herbal compounds.
- Prior to CT and MRI scanning: Obtain MRI Screening Questionnaire (MRI scan days only) Urine HCG test for women of childbearing age.

Response to abnormal results

All clinically abnormal test results will be relayed to participants and/or their referring providers. Participants will be instructed to consult with their physician for follow up and referral to specialists as appropriate. Abnormal lab results may be repeated or reassessed at PI discretion as part of the subject's clinical care.

If ALT, AST, alkaline phosphatase reaches more than 3 times the upper limit of normal without symptoms indicating liver disease or CK is greater than 1000 U/L without muscle symptoms the study drug will be paused and results will be repeated within 2 weeks. Other causes of the abnormalities should also be considered. Restarting the study drug depends on clinical judgment.

ALT, AST, alkaline phosphatase reaching more than 3 times the upper limit of normal or CK >1000 U/L with muscle symptoms will be reported at the time of Continuing Review (see section 8.1).

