3.4 CRITERIA FOR REMOVAL FROM TREATMENT/PROTOCOL

3.4.1 OFF TREATMENT CRITERIA:

Subjects who come off treatment will be returned to usual care for cardiac risk factors as directed by their primary physician. If they consent to continue imaging follow up, they will complete imaging as per protocol.

1. Occurrence of a clinical cardiovascular event including myocardial infarction, acute coronary syndrome, angina, heart failure, stroke or revascularization.
2. Inability to continue on study medications (adverse reaction, not wanting to adhere to the study medications)
3. Elevations of liver enzymes more than three times the upper limits of normal that persists in repeat testing and cannot be explained by other factors than statin use.
4. Myopathy defined as muscle pain with serum creatinine kinase concentrations > 1000 U/L. Any other relevant clinical or laboratory abnormality which cannot be confidently excluded as a side effect from study medications will lead to discontinuation of an individual patient from the trial.

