Software: Sample sizes and stopping boundaries of the group sequential design are computed using the R “gsDesign” package, version 3.1.3 (2015-03-09). Details of the statistical methods and theory of the design are described in C. Jennison and B. W. Turnbull (2000, “Group Sequential Methods with Applications to Clinical Trials”, Chapman and Hall/CRC, Boca Raton, FL).

Figure. Stopping boundaries with one interim look based on the Lan-DeMets O’Brien-Fleming approximate spending function.

Noncompliance and Missing Data: Given our past experience in similar clinical trials, we do not anticipate noncompliance as a major problem. However, despite the best possible effort, there are inevitably noncompliant patients and/or patients with missing data. We categorize the noncompliance and missing data into the following three situations:

- 1) **Noncompliant patients with complete follow-up examinations at baseline and 24 months:** The primary analysis of these patients, including both the interim analysis and the final analysis of the primary endpoint, will be carried out using the intent-to-treat (ITT) principle. Under the ITT principle, the observed plaque volumes at baseline and 24 months from these patients will be included in the primary analysis.
- 2) **Noncompliant patients with missing examinations at 24 months:** Since plaque volume normally does not decrease without significant intervention, we will apply the ITT principle to these patients using the approach of setting their plaque volumes at 24 months to be the same as their baseline values.
- 3) **Compliant patients with missing examination at 24 months:** We expect that only a small portion of the patients will fall into this category, since our study coordinators will give their best efforts to contact and keep track these patients. For the primary analysis, we will include these patients using the same approach as 2) by setting their plaque volumes at 24 months to be the same as their baseline values.

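### Section 3.4.1 opens by letting off-treatment patients keep their imaging but closes by removing some of them from the trial, which can cost an obtainable 24-month scan

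*Combined protocol and SAP*

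**What the plan says.** **3.4.1, opening.** Patients who come off treatment return to usual care. On imaging the text is explicit: "If they consent to continue imaging follow up, they will complete imaging as per protocol".

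**3.4.1, items 1 to 4.** The listed reasons for stopping are a cardiovascular event, inability to continue the medication, liver enzymes above three times the upper limit of normal, and muscle pain with CK above 1000 U/L. The liver item applies only to a rise "that persists in repeat testing and cannot be explained by other factors than statin use".

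**3.4.1, closing sentence.** Printed directly after the myopathy definition, it covers all remaining findings of clinical or laboratory relevance: "which cannot be confidently excluded as a side effect from study medications will lead to discontinuation of an individual patient from the trial".

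**Off-study list (3.4.2).** This separate list names a request by the patient or personal physician, pregnancy or nursing, and investigator discretion. It names no laboratory or adverse-event trigger.

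**3.2, Response to abnormal results.** For symptom-free liver enzymes above three times the upper limit, or symptom-free CK above 1000 U/L, "the study drug will be paused and results will be repeated within 2 weeks". On what happens after that repeat test, the section says: "Other causes of the abnormalities should also be considered. Restarting the study drug depends on clinical judgment".

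**Section 6, Noncompliance and Missing Data.** Noncompliant patients scanned at baseline and 24 months contribute their observed values. Patients without a 24-month scan, compliant or not, are included by "setting their plaque volumes at 24 months to be the same as their baseline values".

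**The concern.** Stopping the drug and leaving the study are different events. In a single-arm trial whose primary endpoint is a 24-month scan, the difference decides whether an outcome is measured. The opening of 3.4.1 keeps them apart and the closing sentence merges them. A coordinator who follows the closing sentence would cancel the remaining scans of a patient who was willing to have them. The analysis would then use an assumed change of zero where a real measurement could have been made. That runs against the intention-to-treat aim in section 6.

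The wording also produces an odd ordering. A patient who has a myocardial infarction or defined myopathy (items 1 and 4) may continue imaging. A patient with a less specific abnormality, whose link to the drug is merely not excluded, may not.

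**Working it through.** The plan gives no figure for this point, so the main check is a comparison of texts. A short calculation then gives the scale per patient.

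**Step 1: which patients the closing sentence reaches.** It applies to any *other* abnormality. Liver enzyme rises have item 3, and CK above 1000 U/L with muscle pain has item 4. The most natural reading leaves both to their own items, although the text does not say so. A symptom-free CK above 1000 U/L does not meet item 4, which requires muscle pain, so it is a clear candidate for the closing sentence.

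**Step 2: follow that patient through the plan.**

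| Event | 3.2 | 3.4.1 opening | 3.4.1 closing |
|---|---|---|---|
| CK above 1000 U/L, no symptoms | Pause, repeat within 2 weeks | – | – |
| Another cause is established | Restart by judgment | – | Not triggered |
| Drug cause cannot be confidently excluded | Restart still by judgment | If drug is stopped, imaging continues on consent | Out of the trial |

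The conflict lies in the last row. 3.2 permits a restart, the opening of 3.4.1 permits imaging without drug, and the closing sentence permits neither.

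**Step 3: effect on the primary endpoint.** Suppose the patient leaves before month 24.

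- Imaging continued: the observed 24-month value enters the analysis.
- Removed from the trial: there is no 24-month scan, so the change is set to zero. Section 6 treats compliant and noncompliant patients alike here, so how this patient is classified does not matter.

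Removal after month 24 leaves the primary endpoint intact and costs the 36-month scan.

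**Step 4: size per patient.** Inputs from section 6 are a mean reduction of 0.008 mL, an sd of 0.03 mL, 190 enrolled and 151 followed to 24 months. If a patient's true reduction is d and it is replaced by zero, the mean reduction falls by d/N.

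- d = 0.008, N = 190: 0.008/190 = 0.000042 mL, which is 1/190 = 0.5% of 0.008 mL.
- d = 0.008, N = 151: 0.008/151 = 0.000053 mL, or 0.7%.
- d two sd above the mean, 0.008 + 0.06 = 0.068, N = 190: 0.068/190 = 0.00036 mL, or 4.5%.
- d two sd below the mean, 0.008 − 0.06 = −0.052, N = 190: −0.052/190 = −0.00027 mL, or 3.4% in the other direction.

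The first two lines assume that a patient taken off drug would still have shown the full average reduction. Such a patient may instead progress, in which case the imputed zero hides the progression. The sign of the effect is therefore unknown.

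**The case against.** The strongest reply is that the sentence is loosely worded and nobody would act on it literally. It stands under a heading about stopping treatment, in a section that opens by preserving imaging, while leaving the study has its own list in 3.4.2. 3.2 handles intolerance by lowering the dose or switching statin, and keeps patients who miss target therapy in the study. For symptom-free CK, 3.2 gives a specific rule that could be taken to prevail. Investigator discretion in 3.4.2 could also cover a justified removal.

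Much of this stands. Stopping treatment is probably what was meant. But no order of precedence is stated, discretion to remove is not a requirement to remove, and if the benign reading is the intended one, the proposed correction simply writes it down.

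A reader might also infer a safety gap: a patient restarted after a liver enzyme rise that cleared off drug has no liver test timed to the restart. That is literally true. Routine tests after month 3 are "annually thereafter when clinically indicated", and "18 and 30 month assessments will be done via telephone, Telehealth platform and or e-mail", with no labs marked at those contacts. Taking 4.348 weeks per month and a restart 2 weeks after the trigger visit, the next marked labs come 52.2 − 13.0 − 2 = 37 weeks after a month-3 restart and 52.2 − 2 = 50 weeks after a month-12 or month-24 restart. A rise found at the conditional month-6 visit gives 26.1 − 2 = 24 weeks.

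The documents do not support calling this a defect. 3.2 provides for labs as clinically indicated, repeats at the investigator's discretion and testing when symptoms appear, and re-exposure after a recent rise is an obvious indication. The label text in section 9 ties its 12-week test to initiation and dose elevation and does not mention restart. A dated post-restart test would be an optional clarification. A new stopping rule for recurrence is not needed, because a recurrence sets off the same pause and repeat again.

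**Conclusion.** The contradiction within 3.4.1 is real and minor. Its consequence is specific: read literally before month 24, the closing sentence turns an obtainable scan into an imputed zero change.

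The documents give no rate for symptom-free CK rises or for other abnormalities that would fall under the sentence, so the total effect cannot be sized. That few patients are involved is a judgment. Each moves the primary mean by about 0.5% of the 0.008 mL target if average, and by at most about 4.5% if within two sd of the mean, under the plan's assumed mean and sd with 190 in the analysis.

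Two stronger readings should be avoided. A reader might size the problem from the label's 1.1% rate of transaminases above three times the upper limit, which gives 190 × 0.011 = 2.1 patients. Those patients most naturally fall under item 3, where imaging stays available, so that count describes a different group. A reader might also infer that the primary result is at risk. Nothing in the documents points to enough affected patients for that.

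**What to change.** 1. In the closing sentence of 3.4.1, replace the ending that removes the patient from the trial with: *discontinuation of study drug, with imaging continued if the patient consents*.
2. Add one sentence to 3.4.1: *Symptom-free elevations of liver enzymes or CK follow the pause, repeat and judged-restart rule in section 3.2; item 3 also applies to liver enzymes.*

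These two edits make 3.4.1 agree with its own opening, with 3.2 and with 3.4.2. They leave the sample size, imaging schedule, imputation rule and primary analysis unchanged. The only running cost is to carry out scans already in the calendar for patients who agree to them.

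Optionally, 3.2 could also name a time for a liver test after any restart. The interval would be a clinical choice, since the documents set none.
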